#### **4. SUBJECT SELECTION AND ENROLLMENT**

This study can fulfill its objective only if appropriate subjects are enrolled. The eligibility criteria are designed to select subjects for whom protocol procedures are considered appropriate.

All relevant medical and non-medical conditions should be taken into consideration, in addition to the inclusion/exclusion criteria below, when deciding if a particular individual is suitable for this protocol.

No type of discrimination (e.g. social class, gender, skin color, ethnicity, etc.) should preclude an eligible subject from participating in the study. Information that is not relevant to the conduct of the study should not be collected.

Prior to any review of personal data, the Informed Consent Document (ICD) should be signed.

##### **4.1. INFORMED CONSENT**

The ICD must be read by the subject and explained to the subject by the PI or designee. The PI or designee must ensure that each study subject is fully informed about the nature and objectives of the study and possible risks associated with participation. After understanding and agreeing, the subject will express her consent to her participation in the study by signing the ICD.

The ICD will be signed and dated by both the PI/designee and by the subject – the signed and dated original will be kept in the Site Master File (SMF) and a signed and dated copy must be given to the subject.

No subject will be evaluated without a signed and dated ICD, which should be kept by the PI as part of the SMF. The ICDs of subjects who are not included in the study will also be part of the SMF.

The ICD must be approved by the Sponsor and the Institutional Review Board/Independent Ethics Committee (IRB/IEC) and must be in compliance with ICH GCP, local regulatory requirements, and legal requirements.

##### **4.2. STUDY POPULATION**

An individual must meet all of the inclusion criteria and none of the exclusion criteria to be included in the study. No waivers to inclusion or exclusion criteria will be permitted.

The inclusion and exclusion criteria will be reviewed for each subject and confirmed by the PI in order to determine subject eligibility.

The PI or designee must ensure that the subject is still eligible through the entire conduct of the study.

#### 4.2.1. Inclusion Criteria

- a) Has read, understood, signed, dated, and received a copy of the Photograph Release and ICD (including a Health Insurance Portability and Accountability Act [HIPAA] disclosure) after the nature of the study has been fully explained.
- b) Female
- c) 35 to 70 years old
- d) Has clinically determined mild to moderate mottled hyperpigmentation on the face at Visit 1, defined as a score of 1-6 on the 10-point Modified Griffiths Scale (see section 7.2.3.3.1), as determined by the PI.
- e) Has clinically determined moderate to severe global facial wrinkling at Visit 1, defined as a score of 4-9 on the 9-point Fitzpatrick Wrinkle and Elastosis Scale (see section 7.2.3.3.1), as determined by the PI.
- f) Fitzpatrick Skin Type I, II, III, IV, V, or VI (an approximately equal number of subjects will be enrolled per skin type per cell; Appendix I).
- g) Able to read, write, speak, and understand English.
- h) Generally in good health based on medical history reported by the subject, as determined by the PI or designee.
- i) Intends to complete the study and is willing and able to fulfill the subject responsibilities (see section 4.2.3).
- j) Meets one of the following criteria:
  - Is not of child-bearing potential or is in a monogamous relationship with a partner who is not of child-bearing potential, meaning the subject and/or partner:
    - Is post-menopausal (amenorrhea for at least 1 year)
    - Had a surgical sterilization (e.g., vasectomy that has been confirmed effective by sperm count check, tubal occlusion, hysterectomy, bilateral oophorectomy or salpingectomy)
  - Must agree to practice a medically acceptable form of birth control during the study and for 30 days after study completion. Female subjects must have used such birth control for at least 3 months prior to study start. Medically acceptable forms of birth control that may be used by the subject and/or partner include:
    - Established use of hormonal methods of contraception (oral, injected, implanted, hormone patch or vaginal ring)
    - Barrier methods of contraception: condom or occlusive cap (diaphragm or cervical/vault caps)
    - Intrauterine device or intrauterine system
    - Abstinence from intercourse that could cause pregnancy. Periodic abstinence (e.g., calendar, ovulation, symptothermal, post-ovulation methods) and withdrawal are not acceptable methods of contraception.

#### 4.2.2. Exclusion Criteria

- a) Has known allergies or has had adverse reactions to common topical skincare products or ingredients in the investigational study materials (see Appendix III).
- b) Has a known light or photosensitivity disorder, or is currently using medication that may cause sensitivity of the skin to light, as determined by the PI or designee based on subject report.
- c) Is currently being treated for skin cancer or has a history of skin cancer.
- d) Presents with a facial skin condition that could interfere with evaluations or confound study results (e.g., moderate to severe rosacea, moderate to severe acne, psoriasis, eczema, atopic dermatitis, solar urticaria, solar hypersensitivity, skin cancer, sunburn, observable suntan, scars, tattoo, etc.).
- e) Has a self-reported uncontrolled metabolic condition or disease, such as diabetes, hypertension, hyper/hypothyroidism, hypercholesterolemia, asthma, epilepsy, etc. Individuals with a controlled health condition may also be excluded from the study at the discretion of the PI or designee.
- f) Has active hepatitis, an immune deficiency disorder (including HIV infection or AIDS), or an autoimmune disease, as reported by the subject.
- g) Is taking immunosuppressive drugs within the 3 months prior to Visit 1 or during the study.
- h) Is currently using, planning to use during the study (other than the investigational study materials), or has used any of the following in the specified time range:

Any of the following topical products on the face: 
 
• Any skin firming, anti-aging, anti-wrinkle, skin lightening products, or any other product or topical known to affect skin aging or dyschromia (products containing alpha/beta/poly-hydroxy acids, vitamin C, soy, Q-10, hydroquinone; topical retinoids, etc.)
 
	1 month prior to Visit 1
Superficial to mid-deep chemical peels or dermabrasion of the face	6 weeks prior to Visit 1
Topical prescription retinoids (e.g. Retin-A®, Retin-A Micro®, Renova®, Avita®, Tazorac®, or Differin®)	4 months prior to Visit 1
Prescription skin lightening products (e.g., hydroquinone, tretinoin, alpha/beta/poly-hydroxyacids, 4-hydroxyanisole alone or in combination with tretinoin, etc.)	4 months prior to Visit 1
Accutane®, Soriatane®, or other oral retinoid	12 months prior to Visit 1
Any of the following on the face: 
 
• Thermage treatments or an equivalent type of high energy treatment
 
• Deep facial chemical peel, non-ablative laser, or fractional laser resurfacing
 
	12 months prior to Visit 1
Facial plastic surgery or ablative laser resurfacing on the face	3 years prior to Visit 1

- i) Female who (to the best of her knowledge) is pregnant, lactating, or planning to become pregnant during the study or within 30 days of study completion.
- j) Intends to begin or change a hormone replacement therapy (HRT) during the study.
- k) Is taking medication for a chronic condition (e.g., insulin, antihistamines, steroidal and non-steroidal anti-inflammatory drugs, antibiotics, etc.) or is taking any other medication that could influence the study results and/or affect the individual's safety, within 30 days before inclusion or during the study.
- l) Has a history of or a concurrent health condition/situation which, in the opinion of the PI or designee may put the individual at significant risk, confound the study results, or interfere significantly with the individual's participation in the study.
- m) Is simultaneously participating in any other clinical study or has participated in any clinical study within 30 days prior to Visit 1.
- n) Is a ward of the court or deprived from liberty by a judiciary or administrative decision.
- o) Is an employee/contractor or immediate family member of the PI, Study Site staff, or Sponsor.

#### 4.2.3. Subject Responsibilities

During the study, the subject responsibilities are as follows:

- Use the provided AM & PM Cleanser twice daily (morning and evening) to wash your full face for the duration of the study.
- Every morning for the duration of the study: after washing and drying your face, apply the provided AM Moisturizer full-face. (If desired, you may use the AM Moisturizer again in the evening [after completing the mask treatment, as applicable]).
- During the 12-week treatment period: every evening after washing and drying your face, use the provided PM Mask Treatment for 10 minutes.
- During the study, do not use any facial cleansers, moisturizers, sunscreens, or light-based devices other than those provided for this study.
- Do not use any exfoliating, sunless tanning, skin lightening, skin firming, or anti-aging products on your face during the study.
- Do not receive any professional or aesthetic facial spa procedures during the study.
- Continue using your regular brands of color cosmetics (i.e. makeup) and makeup remover during the study. Do not start using any new skincare products or change your currently used brands during the study. Use only facial products reviewed by study staff at Visit 1.
- On the day of study visits: remove all leave-on facial products (including eye makeup) and wash with the provided facial cleanser prior to the visit and then do not apply any leave-on facial products until the visit is completed. Note: if you do not follow these directions, you will be asked to remove your makeup/products and wash your face with the provided cleanser on-site prior to the acclimation period.
- Avoid extended periods of sun exposure and all use of tanning beds for the duration of the study. Extra care should be taken to avoid sun exposure from 11 AM to 4 PM.

- Maintain your birth control method for the duration of the study and 30 days after completion.
- If you are using a HRT, do not change it during the study. If you are not using a HRT, do not begin one during the study.
- Attend all scheduled visits.
- Do not begin any other clinical study during the current study.
- Report any side effects, changes in health/medication, pregnancies, issues, or questions to the study staff.
- Bring your study products to all visits. All products must be returned when requested by the Study Site.

See section 6 regarding detailed product usage instructions.

#### **4.3. CONCURRENT PRODUCTS**

Subjects may not use any facial cleansers, moisturizers, sunscreens, or light-based devices other than the provided investigational study materials. They may not use any exfoliating, sunless tanning, skin lightening, skin firming, or anti-aging products on their face during the study, nor should they receive any professional or aesthetic facial spa procedures during the study.

Subjects should continue using their regular brands of color cosmetics (i.e. makeup) and makeup remover during the study. They should not start using any new skincare products or change their currently used brands during the study (for both the face and body). At Visit 1, study staff should record each subject's regular facial products that she will continue to use during the study; during the study, subjects should use only facial products that were reviewed by study staff at Visit 1.

#### **4.4. CONCURRENT MEDICATION**

If a subject is taking any medication during the course of the study or within 1 month prior to the study, it must be recorded as a concurrent (i.e. concomitant) medication. The minimum information that is required is the name of the medication. If this medication is linked to the treatment of an IP-related or study-related AE, the dose and duration of the treatment should be specified. Medications excluded are indicated in section "Exclusion Criteria"; the use of any excluded medication during the study will result in discontinuation of the subject.

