eAdditional IP, auxiliary product, and daily diary units may be dispensed as needed/previous units collected at the Site's discretion.

fSubject disposition will be recorded at final study visit or at the time of subject discontinuation from the study.

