### 7.5.2. Subject Discontinuation

When an individual who has signed the ICD is not included in the study or discontinues/is discontinued prior to completing the study, the reason is to be documented on the Screening and Enrollment Log (or equivalent) and (only for randomized subjects plus screen failed subjects with a reported AE) in the EDC system on the Subject Disposition page. The subject disposition should also be summarized in the final study report. Reasons for subject discontinuation may include:

- Screen Failure (i.e. fails to meet inclusion/exclusion criteria or chooses not to participate)
- Participant is determined to be ineligible after enrollment
- Withdrawal by subject
- Non-compliance with study treatment (including non-compliance with product use/study directions)
- Lack of efficacy
- Protocol deviation/violation (other than non-compliance)
- Death (must be reported in accordance with the reporting requirements defined in the SAE section)
- Other AE/Serious AE (must be reported in accordance with the reporting requirements defined in section 10.3.3)
- Pregnancy (must be reported in accordance with the reporting requirements defined in section 10.3.5)
- Study terminated by Sponsor
- Lost to follow-up
- Other

Subjects may withdraw from the trial at any time at their request, or they may be withdrawn at any time at the discretion of the Sponsor, PI, or designee for safety, behavioral, or administrative reasons. If a subject does not return for a scheduled visit, at least 3 documented attempts will be made to contact the subject in order to establish the reason for withdrawal, and the outcome will be documented. The PI or designee should inquire about the reason for withdrawal, request that the subject return for a final visit, if applicable, and follow-up with the subject regarding any unresolved AEs.

When a subject withdraws from the trial and also withdraws consent for disclosure of future information, no further evaluations should be performed and no additional data should be collected. The PI and staff may retain and continue to use any data collected before such withdrawal of consent.

In case of early subject withdrawal, subjects may be replaced based upon overall enrollment numbers and with the approval of the Sponsor.

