### **8.1. STATISTICAL ANALYSIS POPULATIONS**

██████████ efficacy data will be evaluated for all intent-to-treat (ITT) subjects who used the IP and had baseline and at least one post-baseline data point. AEs will be summarized for all subjects who signed the ICD, differentiating Pre-Treatment Adverse Events (see section 10.3.2.1).

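### Protocol 4.4 takes a randomised woman out of the study for using an excluded medication, with no off-mask follow-up, so her Week 12 primary score may not be collected

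*Protocol*

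**What the plan says.** Protocol 4.4 ends with the rule that "the use of any excluded medication during the study will result in discontinuation of the subject". It allows no exception.

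The exclusion list in 4.2.2 is broad. Exclusion (k) covers drugs for a chronic condition, with antihistamines, anti-inflammatories and antibiotics among the examples. It also reaches "any other medication that could influence the study results and/or affect" the woman's safety, and it applies "within 30 days before inclusion or during the study". Exclusion (b) covers a woman who "is currently using medication that may cause sensitivity of the skin to light". Exclusion (h) covers retinoids. Section 4.2 adds that the investigator must make sure each woman remains eligible throughout the study.

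Discontinuation is a study exit. Table 2, note f, has disposition recorded at the last visit or "at the time of subject discontinuation from the study". Section 7.5.2 asks the site to "request that the subject return for a final visit, if applicable", and neither document maps that visit to Week 12. The only bar on further grading in 7.5.2 is for a woman who leaves and also "withdraws consent for disclosure of future information, no further evaluations should be performed".

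Protocol 8.1 describes the efficacy population as intent-to-treat "subjects who used the IP and had baseline and at least one post-baseline data point". Protocol 8.2.1 and SAP section 5 carry the last score forward if Week 12 global wrinkling is missing in more than 5% of women. SAP Appendix 1 lists missing data as excluded.

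**The concern.** Starting a medication is an event after randomisation. Under 4.4 it ends a woman's participation, and with it the grading that supplies the primary outcome. The Week 12 comparison then uses an earlier score for her or leaves her out. If she is removed before any post-baseline grading, she leaves the efficacy population altogether.

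The protocol gives no reason why grading must stop. Safety may require stopping the mask, for example with a photosensitising drug, but a dermatologist's scoring carries no such risk. The rule is also stricter than the one for poor use of the mask itself: under 7.3 a woman below 90% compliance is either re-instructed or dropped, at the site's discretion after consulting the sponsor. Deciding whether a drug falls under the open part of exclusion (k) takes judgement, but once it does, 4.4 leaves none.

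What is at stake is avoidable missing primary data. Replacement (7.5.2) and over-enrolment (section 5) restore numbers, not the outcomes of the women who were randomised and removed.

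**Working it through.** **The plan's own figure.** Protocol 8.4 gives 92% power for 48 completers per cell, an effect of 0.7 and two-sided 0.05. No standard deviation is stated. Assuming SD = 1, the noncentrality is 0.7 × √(48/2) = 3.43, and the noncentral t with 94 df gives 92.4%, so the figure reproduces. It depends on that SD: 98.9% at 0.8 and 80.7% at 1.2.

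**Allowance for loss.** Protocol section 5 plans about 125 enrolled and 96 finishing: (125 − 96)/125 = 29/125 = 23.2%. This covers all causes up to Week 24, so it does not estimate Week 12 missingness, still less the share due to 4.4.

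**Which missing-data rule applies.** 0.05 × 125 = 6.25, taking all 125 as the denominator. Up to 6 missing (4.8%) means exclusion; 7 or more (5.6%) triggers carrying forward. The total missing from all causes decides this.

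**Carry-forward branch.** Let p be the share removed, equal in both cells, and f the carried-forward effect as a fraction of the Week 12 effect. The estimated difference is 0.7 × [1 − p(1 − f)]. Both p and f are assumptions.

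| f | p = 5% | p = 10% | p = 20% |
|---|---|---|---|
| 1/2 (Week 4 score) | 0.682 | 0.665 | 0.630 |
| 1/3 (Week 4 score) | 0.677 | 0.653 | 0.607 |
| 0 (Week 1 score, no effect yet) | 0.665 | 0.630 | 0.560 |

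**The same calculation under continued grading.** If the retained women stop the mask and keep no benefit by Week 12, the observed difference is 0.7 × (1 − p) = 0.665, 0.630 and 0.560, which equals the last row. Continued grading therefore does not guarantee a larger estimate. It replaces an assumed value with an observed one.

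**Exclusion branch.** With about 62 women per cell, a and b removed in the two cells, and removed women improving d points less than the rest, the bias is (a − b)/62 × d. Assuming d between 0.5 and 1.0:
- 3 and 3 removed: 0
- 4 and 2 removed: 2/62 × d = 0.016 to 0.032
- 6 and 0 removed: 6/62 × d = 0.048 to 0.097

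**Power.** With SD = 1 and 62 per cell, power is 97.2%. Leaving out 5%, 10% or 23.2% of women (58, 55 or 47 per cell) gives 96.2%, 95.3% or 91.9%. Keeping them with no benefit at all gives 95.7%, 93.6% or 84.4%.

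**The case against.** The best counter-argument concerns timing. After Week 4 the next visit is Week 12, so 8 of the 12 treatment weeks fall in that gap. Protocol 7.2.4 lists grading before the closing question on medication changes, so a woman first asked at Visit 5 may already have her primary score. Nothing in the SAP then removes it: there is no per-protocol analysis and no exclusion for deviations. This stands, and it means one cannot infer that every use before Week 12 costs a primary outcome. It does not remove the problem. The listed order is not stated to be binding, women are told to report medication changes, and 7.1 repeats the medication interview at each sub-visit, so use may come to light with graders still to come.

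A second argument is that continued grading has its own cost. Off-mask women may dilute the comparison as much as carrying forward would, as shown above. A retinoid user's improvement could also count towards the within-arm rule in SAP 6.2, which requires the active mask's improvement to exceed 0.5 with no sham comparison. Both points stand, and the fix must deal with the second.

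Third, the intent-to-treat label is qualified in its own sentence, and the SAP calls the set the full analysis set. That is fair: the point is the uncollected score, not the label.

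A reader might also infer that removal differs between cells, because 4.4 mentions drugs given for product-related adverse events. That route is plausible, but the documents give no rates by cell and no difference is shown.

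**Conclusion.** The point holds in a limited form. Section 4.4 requires a study exit, no off-mask follow-up exists, and a woman whose use is identified before her Week 12 grading may have no primary outcome. No stated reason requires that loss.

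Its size cannot be derived from the documents. Apart from 0.7, 125, 96 and the 5% trigger, the inputs to the estimates are assumptions. On those, the carry-forward branch moves 0.7 to between 0.68 and 0.56. The exclusion branch gives a bias from 0 to about 0.10, the top of which needs all six losses in one cell and a full one-point shortfall.

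Two stronger conclusions are not supported. The trial is not shown to lose power, because over-enrolment covers 23.2% loss and even that leaves 91.9% under SD = 1. Nor would the fix be certain to recover 0.7, since women off the mask may lose its benefit. This is an inexpensive improvement that should be made. It is not evidence that the trial's result would be biased.

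**What to change.** 1. **Protocol 4.4.** Replace the last clause with: *Use of an excluded medication after randomization is recorded as a protocol deviation with drug, dose and dates. Mask use stops if the medication may cause photosensitivity or if the PI judges continued use unsafe. Unless she withdraws consent, the subject stays in the study and is graded at all remaining scheduled visits.*
2. **Protocol 7.5.2 and 4.2.** State in 7.5.2 that excluded-medication use is not by itself a reason for discontinuation from the study. State in 4.2 that the continuing-eligibility requirement, and the part of exclusion (k) that applies after entry, govern mask use and not follow-up grading. Without this, the new 4.4 would conflict with 4.2. The criteria for entry do not change.
3. **SAP section 5.** Add that observed Week 12 scores after excluded medication are used in the randomised cell for the active-versus-sham comparison. Add a sensitivity analysis that sets those scores to missing, and report it also for the superiority-to-baseline rule in SAP 6.2, so that a drug acting on wrinkles is not credited to the mask.

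The cost is a few sentences and one sensitivity analysis. No visit is added, because these gradings are already in Table 2. The downside is that some Week 12 scores will be affected by medication or by stopping the mask. A collected score can be set aside later; one never collected cannot be recovered.
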